Further information on these risks (eg, presenting symptoms) can be found in the current version of the durvalumab (MEDI4736) IB. More specific guidelines for their evaluation and treatment are described in detail in the Dosing Modification and Toxicity Management Guidelines (Section 8.4.5). These guidelines have been prepared by the Sponsor to assist the Investigator in the exercise of his/her clinical judgment in treating these types of toxicities. These guidelines apply to AEs considered causally related to the IP/study regimen by the reporting Investigator.

8.3.13 Safety data to be collected following the final data cut-off of the study

For patients continuing to receive IP treatment after final DCO and database closure, it is recommended that the patients continue the scheduled site visits and Investigators monitor the patient's safety laboratory results prior to and periodically during treatment with IP in order to manage AEs in accordance with the durvalumab (MEDI4736) Dosing Modification and Toxicity Management Guidelines (see Section 8.4.5). All data post the final DCO and database closure will be recorded in the patient notes but, with the exception of SAEs, will not otherwise be reported for the purposes of this study.

All SAEs that occur in patients still receiving IP treatment (or within the 90 days following the last dose of IP treatment) post the final DCO and database closure must be reported as detailed in Section 8.4.1.

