Monotherapy or Combination Therapy with Tremelimumab or Tremelimumab Monotherapy),” and is maintained within the Site Master File.

Patients should be thoroughly evaluated and appropriate efforts should be made to rule out neoplastic, infectious, metabolic, toxin, or other etiologic causes of the imAE. Serologic, immunologic, and histologic (biopsy) data, as appropriate, should be used to support an imAE diagnosis. In the absence of a clear alternative aetiology, events should be considered potentially immune-related. In addition, there are certain circumstances in which durvalumab and tremelimumab should be permanently discontinued (see Section 7.1 of this protocol and the TMGs). Following the first dose of IP, subsequent administration of durvalumab and tremelimumab can be modified based on toxicities observed as described in the Dosing Modification and Toxicity Management Guidelines (see the Annex document to this CSP). These guidelines have been prepared by the Sponsor to assist the Investigator in the exercise of his/her clinical judgment in treating these types of toxicities. These guidelines apply to AEs considered causally related to durvalumab monotherapy and the durvalumab + tremelimumab regimen by the reporting Investigator.

Dose reductions are not permitted. In case of doubt, the Investigator should consult with the Study Physician.

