Causality of ‘related’ is made if following a review of the relevant data, there is evidence for a ‘reasonable possibility’ of a causal relationship for the individual case. The expression ‘reasonable possibility’ of a causal relationship is meant to convey, in general, that there are facts (evidence) or arguments to suggest a causal relationship.

The causality assessment is performed based on the available data including enough information to make an informed judgment. With limited or insufficient information in the case, it is likely that the event(s) will be assessed as ‘not related’.

Causal relationship in cases where the disease under study has deteriorated due to lack of effect should be classified as no reasonable possibility.

B 8 Medication error

For the purposes of this clinical study a medication error is an unintended failure or mistake in the treatment process for an AstraZeneca study drug that either causes harm to the participant or has the potential to cause harm to the participant.

A medication error is not lack of efficacy of the drug, but rather a human or process related failure while the drug is in control of the study site staff or participant.

Medication error includes situations where an error.

- Occurred
- Was identified and intercepted before the participant received the drug
- Did not occur, but circumstances were recognised that could have led to an error

Examples of events to be reported in clinical studies as medication errors:

- Drug name confusion
- Dispensing error eg, medication prepared incorrectly, even if it was not actually given to the participant
- Drug not administered as indicated, for example, wrong route or wrong site of administration
- Drug not taken as indicated eg, tablet dissolved in water when it should be taken as a solid tablet
- Drug not stored as instructed
- Wrong participant received the medication (excluding IVRS/IWRS errors)
- Wrong drug administered to participant (excluding IVRS/IWRS errors)

Examples of events that **do not** require reporting as medication errors in clinical studies:

- Errors related to or resulting from IVRS/IWRS – including those which lead to one of the above listed events that would otherwise have been a medication error
- Participant accidentally missed drug dose(s) eg, forgot to take medication
- Accidental overdose (will be captured as an overdose)
- Participant failed to return unused medication or empty packaging

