#### **3.2.3.1 Treatment-Related Adverse Events**

A TRAE is any AE with a relatedness to durvalumab of possible or probable, or where the

relatedness is missing. When the relatedness of an AE is missing on the eCRF, all efforts will be taken to ensure that the Investigator assigns his/her assessment of relatedness prior to database lock. In the tables, listings and figures, the TRAEs are presented as “possibly related adverse events” as per the CRF and AZ standards.

If relatedness of an AE is missing at the DBL, as given in Section 4.1.2, the AE will be considered as related to durvalumab.

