#### **4.1.2 General Considerations for Summary of Safety Data**

The following considerations are for the summary of safety data.

- The missing values in vital signs, laboratory data, coagulation and urinalysis will not be imputed.
- If a laboratory value is reported as <LLQ (where 'LLQ' is the lower limit of quantification), then LLQ value will be used to impute '<LLQ' for the summary tables. In the data listings, this value will be listed as reported <LLQ.
- Any TEAEs with missing causality data will be considered as related to the durvalumab.
- Any partial dates will be presented as reported in the data listings. The partial dates will be imputed for the derivation of time to resolution, time to onset etc. using the criteria given in Section 4.1.3.

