### **4.5 Analysis of Secondary Safety Endpoints**

#### **4.5.1 Adverse Events**

All AEs reported up until 90 days following completion or discontinuation of durvalumab treatment or until the initiation of the first subsequent therapy (whichever occurs first) will be included in the summaries unless explicitly stated otherwise below.

All AEs will be summarised descriptively, in terms of number of patients (n) and percentage of patients (%) reporting the event by MedDRA SOC and PT.

Listings of AEs will include the date of onset, date of resolution (if AE is resolved) and investigator's assessment of severity, relationship to durvalumab, and NCI CTCAE Grade. Separate listings will be produced for all AEs, TRAEs, SAEs, AESIs, imAEs, AEs with outcome of death, AEs leading to discontinuation of durvalumab, AEs leading to discontinuation of study. Listings of AESIs and imAEs will also include the additional information (eg, intervention, dose, duration of therapy etc.) recorded for these AEs. All AEs that are not treatment-emergent will be flagged in the data listings and the time of onset will be flagged as 'pre-treatment', 'post-treatment and no other anti-cancer therapy' and 'after initiation of other anti-cancer therapy'.

An overall summary of AE data will be presented including the number and percentage of patients reporting the following:

- At least one AE

- At least one TRAE
- At least one AE of CTCAE Grade 3 or Grade 4
- At least one TRAE of CTCAE Grade 3 or Grade 4
- At least one SAE
- At least one Serious TRAE
- At least one AE leading to discontinuation of study treatment
- At least one TRAE leading to discontinuation of study treatment
- At least one AE leading to treatment interruption
- At least one TRAE leading to treatment interruption
- At least one AE with outcome of death
- At least one TRAE with outcome of death
- At least one AESI
- At least one TRAE of special interest (AESI)
- At least one imAE (and exact Clopper-Pearson 95% CI)
- At least one immune-mediated TRAEs

The following summaries including the number and percent of patients by SOC and PT will be presented separately:

- All AEs / TRAEs
- All AEs / TRAEs of CTCAE Grade 3 or Grade 4
- All TRAEs of CTCAE Grade 3 or Grade 4 occurring within the six months of first dosed date
- All TRAEs which starts within 90 days after last dose of durvalumab (irrespective of start of subsequent anti-cancer therapy)
- All AEs

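### Appendix B 7 leans poorly documented events towards 'not related', and the six-month Grade 3/4 primary rate has no all-causality counterpart for the same window

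*Protocol*

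**What the plan says.** - **Endpoint.** SAP 3.2.1 and 4.3 define the primary endpoint as the incidence of Grade 3 and 4 TRAEs up to and including Day 183, with a Clopper-Pearson 95% CI, overall and by PS cohort.
- **How causality is obtained.** Protocol 8.3.4 and 8.3.5 collect a yes/no answer to whether there is a reasonable possibility that the product caused the event. Section 8.3.5 sends Investigators to Appendix B 7 to interpret that question.
- **Thin information.** Appendix B 7: "With limited or insufficient information in the case, it is likely that the event(s) will be assessed as" 'not related'.
- **Missing answer.** SAP 3.2.3.1: "If relatedness of an AE is missing at the DBL, as given in Section 4.1.2, the AE will be considered as related to durvalumab". SAP 4.1.2 repeats the rule: "Any TEAEs with missing causality data will be considered as related to the durvalumab".
- **Delayed liver information.** Appendix E 5 says that if the Hy's law work-up is held up beyond 3 weeks, the absence of another explanation is assumed and the case is reported as related until the review is complete.
- **All-causality Grade 3/4 events.** Protocol 9.4 item 2 plans their number and proportion. SAP 4.5.1 lists them in the overall summary and by SOC and PT, and SAP 4.1.1 has safety data summarised by PS group. The six-month table in SAP 4.5.1 covers only related events: "All TRAEs of CTCAE Grade 3 or Grade 4 occurring within the six months of first dosed date".

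**The concern.** The only thing separating an event that counts from one that does not, at the same grade and in the same window, is the Investigator's attribution. The study is open-label and single-arm, and dosing starts within 42 days of radiotherapy. Protocol 4.2.1 itself raises the possibility that radiotherapy makes anti-PD-L1 pneumonitis more likely, so attribution is difficult here.

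If uncertainty tends to be settled as 'no', a badly documented severe event leaves the numerator while the patient stays in the denominator. Nothing planned for the same window would show a reader how much of the severe toxicity was set aside in this way.

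**Working it through.** **1. Follow one poorly documented Grade 3 event through the rules.**
- The Investigator answers 'no', as B 7 says is likely. The field is complete, the SAP missing-data rule does not apply, and the event is not counted.
- The Investigator leaves the field blank and it is still blank at database lock. The SAP rule applies and the event is counted.
- The event is a potential Hy's law case with delayed information. Appendix E makes it related and it is counted if Grade 3 or 4.

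The same lack of information can give a non-event or an event, depending on how the form is completed. (SAP 3.2.3.1 speaks of possible or probable relatedness although the protocol collects yes/no. I read 'yes' as related.)

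**2. Compare what is planned for related and for all-causality Grade 3/4 events.**
- Whole reporting period: n and % for both.
- Up to Day 183: related only.
- Exact 95% CI: among the Grade 3/4 summaries, related only.

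The whole-period figure cannot stand in for the six-month one. SAP 1.3 and 5 time the primary analysis to when the last patient dosed has had the opportunity for six months of treatment, so patients enrolled earlier can contribute events after Day 183.

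**3. Reproduce the plan's precision, then move patients.** The exact limits are the 2.5% quantile of Beta(x, n−x+1) and the 97.5% quantile of Beta(x+1, n−x). The three intervals in SAP 1.3 reproduce: 10/120 gives 4.1 to 14.8%, 12/100 gives 6.4 to 20.0%, and 4/30 gives 3.8 to 30.7%.

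One patient moved changes the rate by 100/n points: 1.0 at n=100, 0.8 at n=120 and 3.3 at n=30. The documents give no misattribution rate, so the counts below are assumptions.
- PS 0 to 1, starting from 12/100 = 12.0% (6.4 to 20.0):
  - 1 lost: 11.0% (5.6 to 18.8)
  - 2 lost: 10.0% (4.9 to 17.6)
  - 3 lost: 9.0% (4.2 to 16.4)
  - 4 lost: 8.0% (3.5 to 15.2; SAP Table 1 prints 15.1 for this upper limit)
- PS 2, starting from 4/30 = 13.3% (3.8 to 30.7):
  - 1 lost: 10.0% (2.1 to 26.5)
  - 2 lost: 6.7% (0.8 to 22.1)

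**4. Check whether the protocol's PACIFIC figures show under-attribution (Protocol 2.2.1).** Any Grade 3/4 AE: 29.9% durvalumab, 26.1% placebo. Related Grade 3/4 AE: 12.0% and 4.7%.
- Patients with a Grade 3/4 AE but none judged related: 29.9 − 12.0 = 17.9 points on durvalumab (17.9/29.9 = 60%) and 26.1 − 4.7 = 21.4 points on placebo (21.4/26.1 = 82%).
- Excess over placebo: 12.0 − 4.7 = 7.3 points for related events and 29.9 − 26.1 = 3.8 points for all events.

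The related excess is larger than the all-causality excess, so these figures give no sign that attribution ran low. They do show that attribution is noisy: under double-blind conditions, 4.7% of placebo patients had a Grade 3/4 event called related.

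**The case against.** The case on the other side is substantial, and most of it stands as a limit on the claim.

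- **A reader might infer that the primary rate is biased low.** The documents do not show that. B 7 predicts how such cases will be assessed and does not instruct. The SAP's missing-means-related rule pushes upward. Missing information is also pursued: Protocol 8.4.1 requires active follow-up of fatal and life-threatening events, 8.3.3 proactive follow-up of all events, and 7.1.1 the use of medical records or the treating physician. Treating part of the 17.9-point PACIFIC gap as misattributed would ignore the placebo arm, where the gap is 21.4 points.
- **A reader might infer that there is no all-causality check at all.** There is one, in Protocol 9.4 and SAP 4.5.1. The listings carry onset date, grade and relatedness, so a Day-183 figure could be derived. It is simply not planned. AESIs are also derived by program from preferred terms (SAP 3.2.3.2), independently of causality.
- **A reader might infer that B 7 and the SAP rule contradict each other.** They cover different situations, an answered question and a blank one, and can operate together. The difficulty is that the conservative rule cannot reach the answered cases.
- **A reader might set B 7 against Protocol 8.4.5.1**, which says: "In the absence of a clear alternative aetiology, events should be considered potentially immune-related". That sentence concerns classification as immune-mediated after a thorough work-up, and is not a general causality default.
- **A reader might infer that a 'no' removes the patient from the toxicity guidelines**, since Protocol 8.3.12 says: "These guidelines apply to AEs considered causally related to the IP/study regimen by the reporting Investigator". But Section 8.2.7 invokes them for suspected pneumonitis with no causality condition, and Section 7.1 allows dosing to stop for an AE on the opinion of the Investigator or sponsor, whatever the attribution.

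It is also fair to say that counting every unclear case as related would bring background post-chemoradiation events into the endpoint. That argues for querying such cases and for showing the all-causality rate, rather than for a different default alone.

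**Conclusion.** The point holds in a limited form. The guide that Investigators are sent to leans unclear cases towards 'not related', the SAP's conservative rule cannot correct an answered 'no', and the plan gives no all-causality Grade 3/4 incidence for the window and with the interval used for the primary result. The primary rate is therefore exposed to downward pressure of unknown size.

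The only firm figure is the sensitivity: 1.0 point per patient at n=100 and 3.3 points at n=30. Losing 4 of 12 at n=100 still leaves the estimate (8.0%) inside the interval planned around 12.0% (6.4 to 20.0), so at plausible counts the effect is within sampling error in the larger cohort. In the PS 2 cohort, 2 of 4 lost halves the estimate. These counts are assumptions. The conclusion rests on Investigators treating B 7 as guidance, which its title and the pointer from Section 8.3.5 make reasonable but do not prove.

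**What to change.** 1. **SAP 4.3.** Add the all-causality Grade 3/4 AE incidence up to Day 183, with the Clopper-Pearson 95% CI, overall and by PS cohort, next to the primary TRAE result. Keep the primary endpoint's other rules (start by Day 183, within 90 days of discontinuation, before subsequent anticancer therapy) and drop only the causality condition. For scale, a 30% rate would read 36/120 = 30.0% (22.0 to 39.0) or 9/30 = 30.0% (14.7 to 49.4). PACIFIC treatment ran to 12 months, so a six-month rate may be lower.
2. **Protocol Appendix B 7, or the eCRF completion guidelines.** Reconcile the sentence with SAP 3.2.3.1 and Appendix E, so that insufficient information leads to a query rather than to a default of 'not related'. A case still unanswered at database lock then falls under the existing SAP rule.

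Enrolment began in Q2 2019, so events already assessed were judged under the present wording. For those, item 1 is the part that helps. The cost is one extra table from data already collected, one reworded sentence, some additional queries, and a related rate that may come out slightly less favourable.

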Appendix C Handling of human biological samples

C 1 Chain of custody of biological samples

A full chain of custody is maintained for all samples throughout their lifecycle.

The Principal Investigator at each centre will keep full traceability of collected biological samples from the patients while in storage at the centre until shipment or disposal (where appropriate).

The sample receiver will keep full traceability of the samples while in storage and during use until used or disposed of or until further shipment and keeps documentation of receipt of arrival.

AstraZeneca will keep oversight of the entire life cycle through internal procedures, monitoring of study sites, auditing or process checks, and contractual requirements of external laboratory providers

Samples retained for further use will be stored in the AstraZeneca-assigned biobanks and will be registered by the AstraZeneca Biobank Team during the entire life cycle.

If required, AstraZeneca will ensure that remaining biological samples are returned to the site according to local regulations or at the end of the retention period, whichever is the sooner.

C 2 Withdrawal of Informed Consent for donated biological samples

If a patient withdraws consent to the use of donated biological samples, the samples will be disposed of or destroyed and the action documented. If samples have already been analysed, AstraZeneca is not obliged to destroy the results of this research.

The Investigator:

- Ensures that AstraZeneca is immediately notified of the patient's withdrawal of informed consent to the use of donated samples
- Ensures that biological samples from that patient, if stored at the study site, are immediately identified, disposed of or destroyed, and the action documented
- Ensures the organisation(s) holding the samples is/are immediately informed about the withdrawn consent immediately and that samples are disposed of or destroyed, the action documented, and the site is informed
- Ensures that the patient and AstraZeneca are informed about the sample disposal.

AstraZeneca ensures the organisation(s) holding the samples is/are informed about the withdrawn consent immediately and that samples are disposed of/destroyed and the action documented and the site is informed.

C 3 International Airline Transportation Association (IATA) 6.2 Guidance Document

LABELLING AND SHIPMENT OF BIOHAZARD SAMPLES

International Airline Transportation Association (IATA) classifies biohazardous agents into 3 categories

(http://www.iata.org/whatwedo/cargo/dangerous_goods/infectious_substances.htm). For transport purposes the classification of infectious substances according to risk groups was removed from the Dangerous Goods Regulations in the 46th edition (2005). Infectious substances are now classified either as Category A, Category B or Exempt. There is no direct relationship between Risk Groups and Categories A and B.

Category A Infectious Substances are infectious substances in a form that, when exposure to it occurs, is capable of causing permanent disability, life-threatening or fatal disease in otherwise healthy humans or animals. Category A pathogens are eg, Ebola, Lassa fever virus:

- Are to be packed and shipped in accordance with IATA Instruction 602.

Category B Infectious Substances are infectious Substances that do not meet the criteria for inclusion in Category A. Category B pathogens are eg, Hepatitis A, B, C, D, and E viruses, HIV types 1 and 2. They are assigned the following UN number and proper shipping name:

- UN 3373 – Biological Substance, Category B
- Are to be packed in accordance with UN3373 and IATA 650

Exempt – all other materials with minimal risk of containing pathogens

- Clinical study samples will fall into Category B or exempt under IATA regulations
- Clinical study samples will routinely be packed and transported at ambient
- Temperature in IATA 650 compliant packaging
(http://www.iata.org/whatwedo/cargo/dangerous_goods/infectious_substances.htm)
- **Biological samples transported in dry-ice require additional dangerous goods specification for the dry-ice content**
- IATA compliant courier and packaging materials should be used for packing and transportation and packing should be done by an IATA certified person, as applicable
- Samples routinely transported by road or rail are subject to local regulations which require that they are also packed and transported in a safe and appropriate way to contain any risk of infection or contamination by using approved couriers and packaging/containment materials at all times. The IATA 650 biological sample containment standards are encouraged wherever possible when road or rail transport is used.

Appendix D CCI

CCI

CCI

CCI

CCI

Appendix E Actions required in cases of increases in liver biochemistry and evaluation of Hy's law

E 1 Introduction

This appendix describes the process to be followed in order to identify and appropriately report cases of HL. It is not intended to be a comprehensive guide to the management of elevated liver biochemistries. Specific guidance on managing liver abnormalities can be found in the Dosing Modification and Toxicity Management Guidelines (Section 8.4.5).

During the course of the study the Investigator will remain vigilant for increases in liver biochemistry. The Investigator is responsible for determining whether a patient meets potential Hy's law (PHL) criteria at any point during the study.

The Investigator participates, together with AstraZeneca clinical project representatives, in review and assessment of cases meeting PHL criteria to agree whether HL criteria are met. HL criteria are met if there is no alternative explanation for the elevations in liver biochemistry other than drug induced liver injury (DILI) caused by the IP.

The Investigator is responsible for recording data pertaining to PHL/HL cases and for reporting AE and SAE according to the outcome of the review and assessment in line with standard safety reporting processes.

E 2 Definitions

Potential Hy's law (PHL)

AST or ALT $\geq 3 \times$ ULN **together with** total bilirubin (TBL) $\geq 2 \times$ ULN at any point during the study following the start of IP irrespective of an increase in alkaline phosphatase (ALP).

Hy's law (HL)

AST or ALT $\geq 3 \times$ ULN **together with** TBL $\geq 2 \times$ ULN, where no other reason, other than the IP, can be found to explain the combination of increases, eg, elevated ALP indicating cholestasis, viral hepatitis, another drug.

For PHL and HL the elevation in transaminases must precede or be coincident with (ie, on the same day) the elevation in TBL, but there is no specified time frame within which the elevations in transaminases and TBL must occur.

E 3 Identification of potential Hy's law cases

In order to identify cases of PHL it is important to perform a comprehensive review of laboratory data for any patient who meets any of the following identification criteria in isolation or in combination:

- ALT $\geq 3 \times$ ULN
- AST $\geq 3 \times$ ULN
- TBL $\geq 2 \times$ ULN

The Investigator will without delay review each new laboratory report and if the identification criteria are met will:

- Notify the AstraZeneca representative
- Request a repeat of the test (new blood draw) by the central laboratory
- Complete the appropriate unscheduled laboratory CRF module(s) with the original local laboratory test result

When the identification criteria are met from central or local laboratory results the Investigator will without delay:

- Determine whether the patient meets PHL criteria (see [Appendix E, E 2](#) for definition) by reviewing laboratory reports from all previous visits (including both central and local laboratory results)

The Investigator will without delay review each new laboratory report and if the identification criteria are met will:

- Notify the AstraZeneca representative
- Determine whether the patient meets PHL criteria (see [Appendix E, E 2](#) for definition) by reviewing laboratory reports from all previous visits
- Promptly enter the laboratory data into the laboratory CRF

E 4 Follow-up

E 4.1 Potential Hy's law criteria not met

If the patient does not meet PHL criteria the Investigator will:

- Perform follow-up on subsequent laboratory results according to the guidance provided in the CSP.

E 4.2 Potential Hy's law criteria met

If the patient does meet PHL criteria the Investigator will:

- Notify the AstraZeneca representative who will then inform the central Study Team

The Study Physician contacts the Investigator, to provide guidance, discuss and agree an approach for the study patients' follow-up and the continuous review of data. Subsequent to this contact the Investigator will:

- Monitor the patient until liver biochemistry parameters and appropriate clinical symptoms and signs return to normal or baseline levels, or as long as medically indicated.
- Investigate the aetiology of the event and perform diagnostic investigations as discussed with the Study Physician.
- Complete the 3 Liver CRF Modules as information becomes available.
- If at any time (in consultation with the Study Physician) the PHL case meets serious criteria, report it as an SAE using standard reporting procedures.

E 5 Review and assessment of potential Hy's law cases

The instructions in this Section should be followed for all cases where PHL criteria are met.

No later than 3 weeks after the biochemistry abnormality was initially detected, the Study Physician contacts the Investigator in order to review available data and agree on whether there is an alternative explanation for meeting PHL criteria other than DILI caused by the IP. The AstraZeneca Global Clinical Lead or equivalent and Global Safety Physician will also be involved in this review together with other subject matter experts as appropriate.

According to the outcome of the review and assessment, the Investigator will follow the instructions below.

If there is an agreed alternative explanation for the ALT or AST and TBL elevations, a determination of whether the alternative explanation is an AE will be made and subsequently whether the AE meets the criteria for a SAE:

- If the alternative explanation is **not** an AE, record the alternative explanation on the appropriate CRF
- If the alternative explanation is an AE/SAE, record the AE /SAE in the CRF accordingly and follow the AstraZeneca standard processes

If it is agreed that there is **no** explanation that would explain the ALT or AST and TBL elevations other than the IP:

- Report an SAE (report term 'Hy's law') according to AstraZeneca Standard processes.
 - The 'Medically Important' serious criterion should be used if no other serious criteria apply
 - As there is no alternative explanation for the HL case, a causality assessment of 'related' should be assigned.

If there is an unavoidable delay of over 3 weeks in obtaining the information necessary to assess whether or not the case meets the criteria for HL, then it is assumed that there is no alternative explanation until such time as an informed decision can be made:

- Report an SAE (report term ‘Potential Hy’s law’) applying serious criteria and causality assessment as per above
- Continue follow-up and review according to agreed plan. Once the necessary supplementary information is obtained, repeat the review and assessment to determine whether HL criteria are met. Update the SAE report according to the outcome of the review amending the reported term if an alternative explanation for the liver biochemistry elevations is determined.

E 6 Actions required when potential Hy’s law criteria are met before and after starting study drug

This Section is applicable to patients with liver metastases who meet PHL criteria on study drug having previously met PHL criteria at a study visit prior to starting Study treatment.

At the first on-study drug occurrence of PHL criteria being met, the Investigator will determine if there has been a significant change in the patients’ condition[#] compared with the last visit where PHL criteria were met.[#]

- If there is no significant change, no action is required.
- If there is a significant change, notify the AstraZeneca representative, who will inform the central Study Team, then follow the subsequent process described in [Appendix E, E 5](#).
- # A ‘significant’ change in the patient’s condition refers to a clinically relevant change in any of the individual liver biochemistry parameters (ALT, AST or TBL) in isolation or in combination, or a clinically relevant change in associated symptoms. The determination of whether there has been a significant change will be at the discretion of the Investigator, this may be in consultation with the Study Physician if there is any uncertainty.

E 7 Actions required for repeat episodes of potential Hy’s law

This section is applicable when a patient meets PHL criteria on study drug, and has already met PHL criteria at a previous on-study treatment visit.

The requirement to conduct follow-up, review, and assessment of a repeat occurrence(s) of PHL is based on the nature of the alternative cause identified for the previous occurrence.

The Investigator should determine the cause for the previous occurrence of PHL criteria being met and answer the following question:

Was the alternative cause for the previous occurrence of PHL criteria being met found to be the disease under study (eg, chronic or progressing malignant disease, severe infection or liver disease), or did the patient meet PHL criteria prior to starting study drug and at first on-study treatment visit, as described in [Appendix E, E 6](#).

If **No**: Follow the process described in [Appendix E, E 4.1](#).

If **Yes**: Determine if there has been a significant[#] change in the patient's condition compared with when PHL criteria were previously met.

If there is no significant change, no action is required.

If there is a significant change, follow the process described in [Appendix E, E 4](#).

A 'significant' change in the patient's condition refers to a clinically relevant change in any of the individual liver biochemistry parameters (ALT, AST or TBL) in isolation or in combination, or a clinically relevant change in associated symptoms. The determination of whether there has been a significant change will be at the discretion of the Investigator; this may be in consultation with the Study Physician if there is any uncertainty.

Appendix F Guidelines for evaluation of objective tumour response using RECIST 1.1 criteria (Response Evaluation Criteria in Solid Tumours)

Introduction

This appendix details the implementation of RECIST 1.1 guidelines ([Eisenhauer et al 2009](#)) for this study with regard to Investigator assessment of tumour burden including protocol-specific requirements for this study. Additional special guidance is provided for determination of confirmation of radiologic progression.

Patients with measurable disease and/or non-measurable and/or NED assessed at baseline by CT/MRI will be entered in this study.

Definitions of measurable, non-measurable, target and non-target lesions

Measurable:

A lesion that can be accurately measured at baseline as ≥ 10 mm in the longest diameter (except lymph nodes which must have short axis¹ diameter of ≥ 15 mm) with CT or MRI and which is suitable for accurate repeated measurements.

Non-measurable:

- All other lesions, including small lesions (longest diameter < 10 mm or pathological lymph nodes with ≥ 10 mm to < 15 mm short axis diameter at baseline²).
- Truly non-measurable lesions include the following: bone lesions, leptomeningeal disease, ascites, pleural/pericardial effusion, inflammatory breast disease, lymphangitic involvement of skin or lung, and abdominal masses/abdominal organomegaly identified by physical examination (manual palpation) that is not measurable by CT or MRI.
- Brain metastasis.

Special cases:

- Lytic bone lesions or mixed lytic–blastic lesions, with identifiable soft tissue components, can be considered measurable if the soft tissue component meets the definition of measurability. Blastic lesions are considered non-measurable.
- Cystic metastases can be considered measurable lesions if they meet the criteria for measurability from a radiological point of view, but if non-cystic lesions are present in the same patient, these should be selected over cystic lesions as TLs.

¹ The short axis is defined as the longest axis perpendicular to long axis.

² Lymph nodes with < 10 mm short axis diameter are considered non-pathological and should not be recorded or followed as NTLs.

Target lesions:

A maximum of 5 measurable lesions (with a maximum of 2 lesions per organ), representative of all lesions involved suitable for accurate repeated measurement, should be identified as TLs at baseline. Lymph nodes, in any location (local/regional and distant), are collectively considered as a single organ, with a maximum of 2 lymph nodes as TLs. A bilateral organ (eg, adrenal glands), a segmented organ (eg, liver), or a multilobed organ (eg, lung) is each considered as a single organ.

A previously irradiated lesion may be selected as a TL, provided that it fulfils the criteria for reproducible measurability and is the only lesion available.

Non-target lesions:

Additional measurable lesions not recorded as TLs and non-measurable lesions (or sites of disease) should be identified as NTLs at baseline.

Imaging modalities:

A summary of the imaging modalities to be used for RECIST 1.1 assessment of TL, NTL, and NLs is provided in [Table 14](#).

Table 14 Summary of imaging modalities for tumour assessment

| Target lesions | Non-target lesions | New lesions |
|-----------------------|---|--|
| CT (preferred) MRI | CT (preferred) MRI Plain X-ray Chest X-ray | CT (preferred) MRI Plain X-ray Chest X-ray Bone scan FDG-PET/CT |

CT: Computed tomography; FDG-PET/CT: 18F-Fluoro-deoxyglucose positron emission tomography/computed tomography; MRI: Magnetic resonance imaging.

CT and MRI

CT and MRI, each preferably with IV contrast, are generally considered to generate the best currently available and reproducible anatomical images for measurement of TL, assessment of NTL, and identification of any NLs.

It is recommended that IV contrast-enhanced CT examinations of the chest and abdomen (including the entire liver and both adrenal glands) will be used to assess tumour burden at baseline and follow-up visits. Any other areas of disease involvement (eg, pelvis, brain) should be additionally imaged based on the signs and symptoms of individual patients. In patients who are sensitive to IV CT contrast, a non-contrast CT examination of the chest and an MRI with IV MRI contrast of the abdomen is appropriate. In patients with severely

compromised renal function a non-contrast CT examination of the chest and abdomen is appropriate. For brain lesion assessment, MRI with IV contrast is the preferred method over IV contrast-enhanced CT. It is strongly recommended to maintain use of the same imaging modality (CT or MRI), acquisition protocol, facility and scanner across all imaging timepoints per patient.

Clinical examination

Clinical examination of skin/surface lesions (by visual inspection or manual palpation) will not be used for RECIST 1.1 assessments. Tumours identified by clinical examination will need to be assessed by correlative CT or MRI anatomical scans.

Chest X-ray

Chest X-ray assessment will not be used for assessment of TL. Chest X-ray can, however, be used to assess NTL and to identify the presence of NLS.

Plain X-ray

Plain X-ray may be used as a method of assessment for bone NTL and to identify the presence of new bone lesions.

Ultrasound

Ultrasound examination will not be used for RECIST 1.1 assessment of tumours as it is not a reproducible acquisition method (operator dependent), is subjective in interpretation and may not provide an accurate assessment of true tumour size. Tumours identified by ultrasound will need to be assessed by correlative CT or MRI anatomical scan.

Endoscopy and laparoscopy

Endoscopy and laparoscopy will not be used for tumour assessments as they are not validated in the context of tumour assessment.

Tumour markers

Tumour markers on cytological or histological (biopsy) samples will not be used for tumour response assessments as per RECIST 1.1.

Histology and cytology

Histology on tumour biopsy samples will not be used as part of the tumour response assessment as per RECIST 1.1.

Results of cytological examination for the neoplastic origin of any effusion (eg, ascites, pericardial effusion, pleural effusion) that appears or worsens during the study will not be used as part of the tumour response assessment in this study. An effusion that appears or

significantly worsens (from trace to large) radiologically by CT/MRI anatomical scans will be considered to be disease progression due to NLs or progression of NTLs, respectively.

Isotopic bone scan

Bone lesions identified on an isotopic bone scan at baseline and confirmed by CT, MRI, or X-ray at baseline should be recorded as NTL and followed by the same method as per baseline assessment.

